3. STUDY PERSONNEL

Patients will be enrolled and data will be collected by an IRB trained Loma Linda emergency medicine advanced practice provider or physicians and Loma Linda student research assistants

4. STUDY INFORMATION

Location(s) of Research Activity: Loma Linda Emergency Department

Expected Start/Stop Dates of Research: July 2017-July 2018

Type of Research: Other- Ultrasound diagnostic

5. INCLUSION / EXCLUSION CRITERIA

Inclusion criteria: Participants may include any patient that is greater than 18 years old with any complaint of vision loss, floaters, and/or any other patient whom the emergency physician feels requires an evaluation for mac on retinal detachment, mac off retinal detachment, vitreous hemorrhage, and or vitreous detachment. Patients that meet this eligibility criterion must also be receiving a consult by a LLU ophthalmology physician in order to obtain comparative time values and accuracy for ED physician diagnosis versus ophthalmologist diagnosis.

Exclusion criteria: Exclusion Criteria includes any ocular trauma, any concern for ruptured globe, or any other extraneous reason determined by the treating ED physician. Excluded patients also include: pregnant women, patients < 18 years of age, and patients not receiving an ophthalmology consult. We will be excluding pregnant women in order to minimize the exposure to ultrasonography for expectant

mothers. We will be excluding patients <18 years of age because it is unlikely that the data from these patients will significantly contribute to our investigation.

6. SUBJECT RECRUITMENT & SCREENING

Number of Subjects: estimated 250-300 across all sites in conjunction with USC, UCI, UCLA

Subject Age Range: 18+

Subject Gender: males and females both

Racial/Ethnic Distribution: any

Target Study Population: Adults non pregnant patients with painless vision loss

Recruitment Method Info: Potential patients will be identified by screening the ED tracking board and by asking physicians working in the department if they have any patients who will be evaluated for a possible retinal detachment.

7. INFORMED CONSENT PROCESS

The study will take place in the Emergency Department of LLUMC. The patient study population will include adult patients presenting to the emergency department with ocular complaints that lead to a physician's suspicion of retinal detachment. A treating attending physician or resident will evaluate the patient as per standard of care. If there is a concern for retinal detachment, the treating physician will order an ophthalmology consult.

IRB trained resident physicians or attending physicians of the Loma Linda emergency department will identify and approach patients regarding the study and obtain a signed informed consent if the patient agrees to participate. No medical records will need to be accessed for the purposes of this screening. If the patient declines to be enrolled in the study, treatment will proceed as per standard of care determined by the treating physician. In the cases where the physician treating the patient approaches the patient about being enrolled in this study, it will be made clear to the patient that his/her decision to be enrolled or not will in no way affect their quality of care in the ED by that physician. Only patients who require an ophthalmology consult to diagnose retinal detachment, as part of their normal ED care, will be enrolled. No x-rays, CTs, or formal ultrasounds will be performed solely for the purpose of this study. If a patient agrees to be enrolled in the study, he/she will sign a written informed consent form and a HIPAA form prior to the ultrasound procedure being performed.

The time of ophthalmology consult will be recorded. Next an emergency department physician will perform the ocular ultrasound and make a diagnosis based upon their findings. Images will be archived and stored in a locked hard drive stored in a locked office. Agreeing to participate will allow the study team to collect data from the ultrasound exam and authorize access to the subject's medical record for the purposes of research only. Information accessed from the medical record includes the duration of symptoms, height and weight, age, and the outcomes of standard testing. The final discharge diagnosis from the ophthalmology consult will be reviewed as well.

8. STUDY DESIGN

- a. *Background or rationale for this study: This is a prospective, cross-sectional study to assess the utility of Point of Care Ultrasound (POCUS) in the diagnosis of ocular complaints in the emergency department with specific focus on the accuracy of diagnosis when compared to that of a blinded ophthalmologist. Ocular complaints represent between 2% and 3% of ED visits (Walker et al, 2011). This percentage may include vision-threatening diagnoses including*

retinal detachment, which can occur in 3-4% of patients presenting with ocular complaints (Alotaibi et al, 2011). However, the equipment and expertise required to adequately assess for conditions such as retinal detachment are limited in busy EDs due to the time consuming and challenging nature of the examination. Incorporating the use of an ultrasound could provide a more available, focused, and timely assessment.

- b. Objectives. To determine the accuracy of ocular ultrasound in diagnosing retinal detachment compared to gold standard of ophthalmology examination.
- c. Procedures involved (Research Interventions): *Ocular Ultrasound*
- d. Alternative procedures, if any, that are not included in the study but might be advantageous to the subject. *none*
- e. If any deception is required for validity of this study, explain why this is necessary and how subject(s) will be debriefed. *n/a*
- f. Concise review of literature that supports the rationale, objectives, and methodology of the proposed study: *Ocular POCUS has been utilized by ophthalmologists for decades and has been described as a tool for identifying retinal detachment since 1969 (Lizzi et al, 2004; Coleman et al, 1969; Vrablik et al, 2014). The ophthalmology team at LLU Medical Center evaluates patients using a focused ocular exam with a fundoscope and ocular dilation. The emergency department team has access to one fundoscope for ocular examination; incorporating the use of an ultrasound could provide a more available, focused, and timely assessment. A recently published meta-analysis identified only 3 small prospective trials in the Emergency Department that were determined to be at low risk of bias (Vrablik, 2014). The first study conducted by Blaivas et al in 2002 demonstrated an impressive 100% sensitivity and 100% specificity of ocular POCUS identification of retinal detachment in 61 subjects. In this study all attending physicians and residents received only 1 hour of hands-on instruction and 1 hour of lecture prior to study participation (Blaivas et al, 2002). A second study conducted in 2010 by Yoonessi et al demonstrated a sensitivity of 100% and specificity of 83% in detecting retinal detachment by ocular POCUS in 48 subjects after only a 20-minute ocular ultrasound lecture (Yoonessi et al, 2010). Shinar et al conducted the final study in 2011, which demonstrated a sensitivity of 97% and specificity of 92% in detecting retinal detachment by ocular POCUS in 92 subjects (Shinar et al., 2011). These studies suggest that ocular POCUS is an accurate diagnostic tool for identifying retinal detachment in the ED and may require minimal ED physician training. However, these studies are limited in their sample size. We intend to expand upon this prior research by enrolling more patients in addition to comparing the accuracy of ocular POCUS diagnosis to a blinded ophthalmologist. In secondary outcome measures we will compare the overall time to diagnosis of the Emergency Physician performing ocular POCUS to the time to diagnosis of the consulting ophthalmologist. Many additional studies have identified multiple other diagnostic utilities for ocular ultrasound. While accurate assessment of the optic disc can provide critical information regarding the patient's intracranial pressure, and be invaluable in diagnosis and treatment for patients, an accurate evaluation by fundoscopic examination is challenging at best and often impossible for those without specific expertise. Utilizing ultrasound to assess both retrobulbar optic nerve sheath and optic disc swelling as an indicator of increased intracranial pressure may prove as an*

accurate alternative. This may lead to earlier ED detection of increased intracranial pressure that may be caused by a variety of pathologies including inflammatory diseases, infection, infiltrative conditions, and microvascular infarction, such as occurs with malignant hypertension (Blaivas, 2003; Tayal et al, 2007; Kimberly et al, 2008; Geeraerts et al, 2008, Teismann et al, 2013). Other case reports recently suggest the potential utilization of ultrasound to identify optic neuritis and as risk stratification for identifying orbital cellulitis (Kang et al, 2014). Therefore, continuing to expand the research of ocular POCUS in the ED could lead to a multitude of uses for the evaluation of ocular complaints that may improve the accuracy and speed to diagnosis at a lower cost with a non-invasive diagnostic tool.

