9. DATA COLLECTION

Potential study subjects will be identified by participating researchers by a complaint of painless vision loss and treating physician's clinical suspicion of retinal detachment for which an ophthalmology consult is ordered. If a patient meets criteria for the study, then a research team member will approach each patient who meets criteria for possible enrollment. The patient will be given a Consent Form to read and any questions answered by the enrolling and/or treating physician. If he or she agrees to participate in the study, the patient will sign a HIPAA Authorization Form and Consent Form prior to enrollment. The emergency physician will evaluate the patient as per standard of care. Inclusive criteria for this study denotes that patients must be receiving an ophthalmology consult as per standard of care. The time of ophthalmology consult will be recorded. The ocular point of care ultrasound will then be performed on the patient while a research team member (including research assistant students) records required information on a data collection form. The ultrasound that will be performed will be for research purposes in the majority of cases. The treating physician may perform an ocular ultrasound on the patient as part of the treatment plan, per physician preference. In this case, the patient will still need to consent to the use of their ultrasound data for research. The physician performing the ultrasound will place the probe over the patient's closed eye. The physician will perform two exams, a static exam and a kinetic exam. In the static exam the physician will ask the patient to keep their eyes forward while they scan longitudinal and transverse in long and short axis (all in normal gain). Then for the kinetic exam, the physician will use normal gain to visualize the ocular nerve in longitudinal axis, then the physician will over gain for the same visualization. The PHI recorded will be the medical record number, name of the patient, and date and time of treatment. Only the lead researcher and co-researchers will have access to the medical record number for reviewing ultrasound reports and disposition reports, as indicated on the attached Data Collection Sheet. The final diagnosis of the ophthalmologist will be accessed through the use of the medical record number. The time it was entered in the chart will be used as the time parameter for which we use as the ophthalmologist consult time. Patient privacy will be protected during this study as the patient information will be coded and replaced with a study number that will be used during the study. This information will be kept in a locked area and separate from the study files, only authorized members of the study team will have access to patient identifiable data. Subject identifiable information will be destroyed once the data is no longer needed. Regarding training, ED residents will receive supplemental lecture and hands-on training in ocular ultrasound. The purpose of this supplemental training will be to familiarize residents with performing an ocular ultrasound. The training itself will not be evaluated in practice for research purposes.

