11. DATA ANALYSIS

The data will be screened for normality, missing data, outliers, and skewness. Descriptive statistics will be conducted on the data, including all study related variables. Correlation matrices and path analyses will be presented to examine the mediating role. Effect sizes for all of these statistics will be reported to establish practical significance.

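### The time-to-diagnosis comparison takes no account of whether the POCUS diagnosis was correct, so it cannot show faster correct diagnosis

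*Combined protocol and SAP*

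**What the plan says.** The main objective (section 8, item b) is accuracy: "To determine the accuracy of ocular ultrasound in diagnosing retinal detachment compared to gold standard of ophthalmology examination". Item f of the same section adds the secondary outcome: "we will compare the overall time to diagnosis of the Emergency Physician performing ocular POCUS to the time to diagnosis of the consulting ophthalmologist".

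Three other places fix what enters that comparison:

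- Section 7, on the emergency side: "Next an emergency department physician will perform the ocular ultrasound and make a diagnosis based upon their findings". There is no confirmation step.
- Section 9, on the ophthalmology side, speaking of the final diagnosis: "The time it was entered in the chart will be used as the time parameter for which we use as the ophthalmologist consult time".
- Section 5 requires a consult for every patient, "in order to obtain comparative time values and accuracy for ED physician diagnosis versus ophthalmologist diagnosis". Time and accuracy are both wanted from the same patients, but nothing links them.

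Section 11 contains no analysis of time to diagnosis. Apart from data screening, descriptive statistics and effect sizes, it offers only this: "Correlation matrices and path analyses will be presented to examine the mediating role".

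**The concern.** The two times do not measure the same thing. The ophthalmologist's time is the time at which the reference diagnosis is available. The emergency physician's time is the time at which some diagnosis is available, right or wrong. Where the two disagree, the correct diagnosis exists only once the ophthalmologist has given it, so nothing was gained on the way to it. That patient nevertheless enters the comparison with the early POCUS time.

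The outcome therefore responds to speed alone: a reader who concludes sooner does better on it whatever the error rate. Someone using this trial to judge POCUS in the emergency department would want to know whether the right answer came sooner, and this comparison does not tell them. The issue is separate from which clock events start and stop each time.

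**Working it through.** The plan states no expected times, standard deviation, effect size or hypothesis for this outcome, so there is no figure to reproduce. The definition was checked by reading, and its possible size by arithmetic.

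**Reading.** Sections 5, 7, 8, 9 and 11 were compared for any rule that restricts the comparison to diagnoses agreeing with the reference, treats disagreeing ones differently, or tabulates times by correctness. None has one. Inclusion of wrong diagnoses follows from an unconditional definition; it is not stated outright.

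**Inputs.**
- Sensitivity (Se) and specificity (Sp) for retinal detachment, from the three prospective studies cited in section 8, item f: 100%/100% (61 subjects), 100%/83% (48 subjects), 97%/92% (92 subjects).
- Planned size, section 6: "estimated 250-300 across all sites in conjunction with USC, UCI, UCLA".
- Prevalence p among enrolled patients: not given. Section 8, item a, gives 3-4% among all ocular complaints, which is a wider population than patients with suspected detachment and a consult. Assumed here: 20% to 40%, with 3.5% to 50% as a wide check.

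**Wrong share.** w = p(1 - Se) + (1 - p)(1 - Sp). At p = 0.30:
- 97%/92%: 0.30 × 0.03 + 0.70 × 0.08 = 0.009 + 0.056 = 6.5%
- 100%/83%: 0.30 × 0 + 0.70 × 0.17 = 11.9%

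| Se/Sp | p = 20% | p = 30% | p = 40% |
|---|---|---|---|
| 100%/100% | 0% | 0% | 0% |
| 97%/92% | 7.0% | 6.5% | 6.0% |
| 100%/83% | 13.6% | 11.9% | 10.2% |

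The two imperfect studies thus span 6.0% to 13.6%. That is 15 to 34 patients of 250 (250 × 0.060; 250 × 0.136), or 18 to about 41 of 300. Over p = 3.5% to 50% the span is 5.5% (97%/92% at 50%) to 16.4% (100%/83% at 3.5%), about 17 to 49 of 300.

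**Effect on the mean.** Let Dc and Dd be the mean time differences (ophthalmologist minus POCUS) in concordant and discordant patients.
- All diagnoses: (1 - w)Dc + wDd.
- Time gained to a correct diagnosis, with zero for discordant patients: (1 - w)Dc.
- Excess: wDd.

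If Dd = Dc = D, the excess is wD out of D, so the overall mean is overstated by the share w of itself. As a ratio this is 1/(1 - w): 1/0.940 = 1.06 to 1/0.864 = 1.16 over 20-40% prevalence, and about 1.06 to 1.20 over the wide range. If Dd differs from Dc, the excess changes in proportion to Dd.

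**The case against.** The strongest reply is that accuracy is the main objective and is measured in the same patients. A hasty, inaccurate reader would be exposed there, and reporting speed and accuracy side by side is a legitimate choice. This stands in part: the data would allow a breakdown by correctness. But a two-by-two table of diagnoses does not correct a mean time difference that includes the wrong ones, and no breakdown is planned.

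It can also be said that the effect is modest and rests on assumptions. That stands. It is nil if POCUS is perfect, prevalence is assumed, and so is independence of the time gap from correctness. Under that independence, giving discordant patients a zero difference shrinks a positive mean but cannot reverse it. Every enrolled patient has the consult anyway, so any gain in time is hypothetical even for correct diagnoses. A composite of speed and accuracy is also harder to interpret than the two apart, which argues for adding it rather than substituting it.

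Two stronger readings are tempting and should be resisted. A reader might infer that the plan awards wrong diagnoses a time gain. It does not say so: it says only that times will be compared, defines no gain, and is silent on discordant cases. A reader might also take the phrase "improve the accuracy and speed to diagnosis at a lower cost" at the end of section 8, item f, as a claim to be drawn from this outcome. It closes a discussion of other uses of ocular ultrasound and expresses a hope about further research.

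Finally, the lack of a visible time stamp for the POCUS diagnosis and of a stated common start time are separate gaps, arguably prior to this one.

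**Conclusion.** The point holds as a gap in the definition of a secondary outcome. The comparison ignores whether the POCUS diagnosis was correct, while its comparator is the reference diagnosis, so it cannot support a statement about faster correct diagnosis.

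The likely distortion is modest. It is 0% of the mean difference under one cited study and 6.0% to 13.6% under the other two, given 20-40% prevalence, cited accuracies that carry over to this trial, and a time gap unrelated to correctness. Its direction favours POCUS whenever the discordant POCUS diagnoses come, on average, before the ophthalmologist's. Its size in minutes cannot be worked out because no times are given. These figures cover detachment present or absent only. Section 5 also names macular status, vitreous hemorrhage and vitreous detachment; scoring those could raise the discordant share, but the documents give no accuracy for them. The accuracy objective is not affected.

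**What to change.** In the outcome statement (section 8, item f) and in section 11, specify in advance that:

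1. The time comparison is reported separately for patients whose POCUS diagnosis agrees and disagrees with the reference on retinal detachment, with the number discordant.
2. A time-to-correct-diagnosis analysis is added, in which concordant patients keep their POCUS time and discordant patients take the ophthalmologist's time. The all-diagnoses comparison stays beside it.
3. Any statement about faster diagnosis rests on these concordance-aware results.

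The cost is a little more analysis and probably a slightly smaller stated time difference. No extra patients or procedures are needed. One condition must be checked: the data collection form must record when the POCUS diagnosis was made. The form is not in the file and the visible text names no such time stamp; if it is missing, it has to be added. Discordant patients would also inherit the ophthalmologist's chart-entry time, which may fall after the actual diagnosis, and the report should say so.

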9. DATA COLLECTION

Potential study subjects will be identified by participating researchers by a complaint of painless vision loss and treating physician's clinical suspicion of retinal detachment for which an ophthalmology consult is ordered. If a patient meets criteria for the study, then a research team member will approach each patient who meets criteria for possible enrollment. The patient will be given a Consent Form to read and any questions answered by the enrolling and/or treating physician. If he or she agrees to participate in the study, the patient will sign a HIPAA Authorization Form and Consent Form prior to enrollment. The emergency physician will evaluate the patient as per standard of care. Inclusive criteria for this study denotes that patients must be receiving an ophthalmology consult as per standard of care. The time of ophthalmology consult will be recorded. The ocular point of care ultrasound will then be performed on the patient while a research team member (including research assistant students) records required information on a data collection form. The ultrasound that will be performed will be for research purposes in the majority of cases. The treating physician may perform an ocular ultrasound on the patient as part of the treatment plan, per physician preference. In this case, the patient will still need to consent to the use of their ultrasound data for research. The physician performing the ultrasound will place the probe over the patient's closed eye. The physician will perform two exams, a static exam and a kinetic exam. In the static exam the physician will ask the patient to keep their eyes forward while they scan longitudinal and transverse in long and short axis (all in normal gain). Then for the kinetic exam, the physician will use normal gain to visualize the ocular nerve in longitudinal axis, then the physician will over gain for the same visualization. The PHI recorded will be the medical record number, name of the patient, and date and time of treatment. Only the lead researcher and co-researchers will have access to the medical record number for reviewing ultrasound reports and disposition reports, as indicated on the attached Data Collection Sheet. The final diagnosis of the ophthalmologist will be accessed through the use of the medical record number. The time it was entered in the chart will be used as the time parameter for which we use as the ophthalmologist consult time. Patient privacy will be protected during this study as the patient information will be coded and replaced with a study number that will be used during the study. This information will be kept in a locked area and separate from the study files, only authorized members of the study team will have access to patient identifiable data. Subject identifiable information will be destroyed once the data is no longer needed. Regarding training, ED residents will receive supplemental lecture and hands-on training in ocular ultrasound. The purpose of this supplemental training will be to familiarize residents with performing an ocular ultrasound. The training itself will not be evaluated in practice for research purposes.

Only the lead researcher and co-researchers will be using the medical record number for accessing patient information and reports.

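### Could a treatment scan made before the ophthalmology consult is ordered enter the accuracy data and bias it?

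*Combined protocol and SAP*

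**What the plan says.** Section 7 (Informed Consent Process) sets out a sequence. It starts with the clinical evaluation: "A treating attending physician or resident will evaluate the patient as per standard of care". The referral comes next: "If there is a concern for retinal detachment, the treating physician will order an ophthalmology consult". Consent and the HIPAA form must be signed before the scan, and then: "The time of ophthalmology consult will be recorded. Next an emergency department physician will perform the ocular ultrasound".

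Section 9 (Data Collection) follows the same sequence. Candidates are patients for whom a consult has been ordered on suspicion of retinal detachment. Then "If a patient meets criteria for the study, then a research team member will approach each patient who meets criteria for possible enrollment", consent is taken, the consult time is noted, and the ultrasound is done while a research team member fills in the data form.

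Directly after this, section 9 says that most scans will be made for research and adds: "The treating physician may perform an ocular ultrasound on the patient as part of the treatment plan, per physician preference". The condition attached is "In this case, the patient will still need to consent to the use of their ultrasound data for research".

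Section 5 (Inclusion / Exclusion Criteria) excludes "patients not receiving an ophthalmology consult".

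**The concern.** The sentence on treatment scans has no time point, and its only stated condition is consent to data use, which could be read as covering a scan already made. The treating physician may also be the recruiter, since section 7 provides for this: "In the cases where the physician treating the patient approaches the patient about being enrolled in this study". Suppose that physician scans during the evaluation, before deciding on a consult. The result could then feed the concern that triggers the consult, and the consult is required for enrolment.

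This is the setting for partial verification bias. If scan-negative patients are referred less often, false negatives and true negatives drop out. Apparent sensitivity rises unless it is truly 100%, and apparent specificity falls unless it is truly 100%. The study's only stated objective is accuracy against the ophthalmology examination, and a bias of this kind does not shrink as more patients are enrolled.

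**Working it through.** **Text.** The documents contain no figure to reproduce, so the first check is the order of steps.

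| Step | Section 7 | Section 9 |
|---|---|---|
| Consult ordered | After the evaluation, if detachment is a concern | Part of how candidates are identified |
| Consent | Signed before the ultrasound | Signed before enrolment |
| Consult time | Recorded before the ultrasound | Recorded before the ultrasound |
| Ultrasound | Next step | Next step, with a research team member recording |

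The treatment-scan sentence comes right after the statement that most scans are for research. Read in place, it distinguishes the purpose of the scan at that step and does not open an earlier time point. A scan made before the patient was identified and approached would ordinarily lack the research team member who completes the form. No passage admits such a scan, and none bars it by name.

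**Size if such scans were used anyway.** Inputs:

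- True accuracy: sensitivity (Se) 97% with specificity (Sp) 92%, and 100% with 83%, from two of the earlier studies cited in section 8.
- Assumed: detachment prevalence π = 0.20.
- Assumed: p, the share of enrolled scans that are treatment scans made before the order, 5% to 25%.
- Assumed: v, the entry rate of scan-negatives relative to scan-positives in that subset, 0.25 to 0.8.

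Formulas, with cells in the order TP, FN, FP, TN:

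- Scans in the stated order: A = (π·Se, π·(1−Se), (1−π)·(1−Sp), (1−π)·Sp).
- Scans before the order: B = (TP, v·FN, FP, v·TN), rescaled to sum to 1.
- Enrolled mix: M = (1−p)·A + p·B.
- Apparent Se = M_TP/(M_TP+M_FN); apparent Sp = M_TN/(M_TN+M_FP).

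Worked case, 97/92 with v = 0.5 and p = 0.10:

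- A = (0.194, 0.006, 0.064, 0.736).
- B before rescaling = (0.194, 0.003, 0.064, 0.368), sum 0.629; after rescaling (0.3084, 0.0048, 0.1017, 0.5851).
- M = (0.2054, 0.0059, 0.0678, 0.7209).
- Apparent Se = 0.2054/0.2113 = 97.2%; apparent Sp = 0.7209/0.7887 = 91.4%.

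Apparent values (%) over the grid:

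| True Se/Sp | v | p = 5% | p = 10% | p = 25% |
|---|---|---|---|---|
| 97/92 | 0.8 | 97.03/91.91 | 97.07/91.83 | 97.16/91.56 |
| 97/92 | 0.5 | 97.11/91.71 | 97.22/91.41 | 97.51/90.48 |
| 97/92 | 0.25 | 97.23/91.37 | 97.44/90.72 | 97.95/88.64 |
| 100/83 | 0.8 | 100/82.84 | 100/82.67 | 100/82.18 |
| 100/83 | 0.5 | 100/82.47 | 100/81.93 | 100/80.28 |
| 100/83 | 0.25 | 100/81.93 | 100/80.84 | 100/77.38 |

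Prevalence matters little: 97/92 with p = 25% and v = 0.25 gives 98.0/88.2 at π = 0.10 and 97.8/89.3 at π = 0.40. With v = 1 there is no bias.

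Outer case: section 9 says most scans are for research, so treatment scans are under half. If every one preceded the order (p = 49%) and v = 0.25, the results are 98.5/84.9 and 100/71.2.

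**Sampling error for scale.** Section 6 plans 250–300 patients. Assume 250, of whom 50 have a detachment and 200 do not. The 95% half-widths are:

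- Sensitivity 97%: 1.96·√(0.97·0.03/50) = 4.7 points.
- Specificity 92%: 1.96·√(0.92·0.08/200) = 3.8 points.
- Specificity 83%: 1.96·√(0.83·0.17/200) = 5.2 points.

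On the 5–25% grid the shift exceeds the half-width in one corner only: 100/83 with p = 25% and v = 0.25, where 83 − 77.4 = 5.6 points against 5.2.

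**The case for a change.** The strongest case for acting is that the text really is silent on this scan. Consent to the use of data is worded loosely enough to cover a scan already done, section 11 (Data Analysis) has no rule on which scans count, and section 6 names several institutions that might apply an unstated rule differently. Clarifying would be cheap, and a shift in the estimate is not excused by wide confidence intervals. The timing might also be hard to recover later, because section 9 takes the charting of the ophthalmologist's diagnosis as the consult time, which is not the time of the order.

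The silence is real, and so is the point about consult time. What does not stand is the step from silence to bias. It needs a treating physician to scan before the order, the result to lower referral, and the team then to use that scan against the order stated in two sections. The documents assert none of these. Sections 7 and 9 base the referral on clinical concern or suspicion and do not mention ultrasound in that decision.

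A clarifying sentence would also gain little. If the stated order is applied to every study scan, a comparison with and without earlier scans has nothing to compare. If an early scan did sway the referral, the patient stays selected even when scanned again in the right order, so a rule on which scan counts would not remove that selection. The data collection sheet and the consent form are not in the text and may already settle the timing.

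**Conclusion.** The concern does not call for a change. It is literally true that section 9 gives no time point for a treatment scan, but the order in sections 7 and 9, read as written, keeps scans made before the consult order out of the study data. An analyst would fill the gap that way. The size of any bias cannot be derived from the documents, since p, v and prevalence are all assumed. Over the 5–25% grid the shift is 0.03 to 0.95 points in sensitivity and 0.1 to 3.4 in specificity for the 97/92 pair, and 0 and 0.2 to 5.6 for the 100/83 pair. The outer case gives larger shifts, but it requires every treatment scan to precede the order, for which the text gives no basis. The conclusion rests on the stated order being followed. If scans made before the order were in fact accepted as study data, the question would have to be looked at again.
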